1.4 Investigational products

CCNU and TMZ are both commercially available drugs approved for marketing authorization in Germany. The SmPCs of CCNU/ Temozolomide are attached to the study protocol in Appendix 5. In this study CCNU is used in label. Temozolomide is only approved to be given in a monotherapy. Since in the experimental arm a combined therapy consisting of Lomustine + Temozolomide is provided, Temozolomide in the experimental arm is used off label. This combined therapy has been used before in a non-randomized clinical trial leading to an improved survival by acceptable toxicity ([name] et al 2006), thereby justifying the combination of both drugs and establishing the rational for this clinical trial (for details see chapter 1.1-1.3).

1.4.1 Temozolomide

Chemistry

TMZ (3, 4-dihydro-3-methyl-4-oxoimidazole [5,1-d-as-tetrazine-8-carboxamide]; C₆H₆N₆O₂, molecular weight 194.15) is an imidazotetrazinone compound that is spontaneously hydrolyzed under physiological conditions to yield the active metabolite, 5-(3-methyltriazen-1-yl)imidazole-4-carboxamide (MTIC).

Pharmacodynamics

Temozolomide is a base-selective DNA-methylating agent with a preference for the N⁷ and O⁶ positions of guanine. Although methylation at O⁶ accounts for no more than 5-10% of DNA lesions, O⁶ methylation is considered a major mediator of TMZ cytotoxicity because it promotes the substitution of cytosine by thymine upon replication which triggers the DNA mismatch repair system. The DNA repair enzyme MGMT transfers methyl groups from the O⁶ position of guanine to a cysteine moiety in its active center, but is thereby inactivated and consumed, and cannot be recovered. Accordingly, cells with high MGMT levels are predicted to resist TMZ cytotoxicity unless their MGMT activity is either depleted e.g. by continuous TMZ exposure or MGMT is inhibited pharmacologically. It is assumed that the futile attempts at DNA repair in cells lacking MGMT contribute to the overall cytotoxic effects of TMZ, but this has not been confirmed in a clinical setting (Friedman et al. 1998).

Pharmacokinetics and metabolism

TMZ has an oral bioavailability of almost 100% and does not require hepatic activation, resulting in reliable drug exposure after oral administration. The drug should be taken early in the morning prior to the first meal since concurrent meals reduce absorption by approximately 10% (Brada et al., 1999). The serum half-life is less than 2 h. TMZ is rapidly eliminated with a mean elimination half-life of 1.8 hours and exhibits linear kinetics over the therapeutic dosing range. TMZ has a mean apparent volume of distribution of 0.4 L/kg (%CV=13%). It is weakly bound to human plasma proteins; the mean percent bound of drug-related total radioactivity is 15%. Blood brain barrier penetration is good, and the cerebrospinal fluid levels reach 20-40% of the serum levels (Ostermann et al. 2004). Drug accumulation has not been observed.

TMZ is spontaneously hydrolyzed at physiologic pH to the active species, 3-methyl-(triazen-1-yl)imidazole-4-carboxamide (MTIC) and to TMZ acid metabolite. MTIC is further hydrolyzed to 5-amino-imidazole-4-carboxamide (AIC), which is known to be an intermediate in purine and nucleic acid biosynthesis and to methylhydrazine, which is believed to be the active alkylating species. Cytochrome P450 enzymes play only a minor role in the metabolism of temozolomide and MTIC. Relative to the AUC of TMZ, the exposure to MTIC and AIC is 2.4% and 23%, respectively. About 38% of the administered TMZ total radioactive dose is recovered over 7 days; 37.7% in urine and 0.8% in feces. The majority of the recovery of radioactivity in urine is as unchanged TMZ (5.6%), AIC (12%), TMZ acid metabolite (2.3%), and unidentified polar metabolites(s) (17%). Overall clearance of TMZ is about 5.5 L/hr/m²

Side effects

Temozolomide can cause myelosuppression. Thrombocytopenia and lymphopenia might occur. Lymphopenia can lead to opportunistic infection, e.g. pneumocystis carinii pneumonia. Further, medication with temozolomide might lead to nausea and vomiting. Some patients suffer from diarrhea during the first applications. Rare side effects include headache, fatigue, obstipation, exanthema, fever and shivering, pain, vertigo, weight loss, dyspnea, dyspepsia, alopecia, abnormal tasting, paresthesia as well as allergic reaction including erythrodermia, urticaria and anaphylactic shock. Any specific toxicity in distinct organs has not yet been reported. (Reversible) elevated liver enzymes have been described as potential side effect.

1.4.2 CCNU

Chemistry

CCNU (lomustine, 1-(2-chloroethyl)-3-cyclohexyl-1-nitrosourea) is a nitrosourea compound that -in humans- undergoes biotransformation to the geometric, monohydroxylated metabolites trans-4-hydroxy CCNU and cis-4-hydroxy CCNU. CCNU interacts with DNA by alkylation and carbamoylation (Lown et al., 1979), particularly with deoxyguanosine and deoxycytidine (Gombar et al., 1980), and carbamoylation of free amino groups of peptides and proteins (Wheeler et al., 1975).

Pharmaceutical interactions

CCNU is hydroxylized in the liver to active metabolites. Hydroxylation is dependent on cytochrome P450 enzymes. Thus, substances influencing cytochrome P450-dependent metabolism are likely to influence the metabolism of CCNU. Interactions of CCNU with activation of ifosfamid and cyclophosphamid are known (Chang et al., 1994). Of importance is a retrospective observational trial indicating a reduced survival in glioblastoma patients treated with CCNU when cytochrome P450 enzyme inducing antiepileptics (e.g. Phenytoin, Carbamazepin) were administered (Oberndorfer et al., 2005). Thus, the present trial requires to switch patients with EIADs on non-enzyme-inducing antiepileptics.

Distribution and pharmacokinetics

Because of the rapid chemical and biochemical decomposition and oxidative transformation of CCNU in plasma and tissues shortly after administration, distribution data, based on experiments with CCNU labeled with ¹⁴C in either the ethylene, carbonyl, or cyclohexyl moieties refer to hydrolysis products rather than intact CCNU. After oral administration of variously labeled CCNU in man, radioactivity was demonstrated within 10 minutes in plasma, with peak levels in 1-6 hours (Sponzo et al., 1973). Significant quantities of radioactivity are found in all tissues including brain and cerebrospinal fluid within a short time and are similar regardless of position of label or route of administration. The decomposition of CCNU is markedly increased in the presence of proteins (Levin et al., 1978); the mechanism appears to be catalysis by serum albumin of the conversion of CCNU to reactive species. The cyclohexyl ring is subject to oxidation. Preferential distribution is to fat, liver, and brain (Oliverio et al., 1970; Litterst et al., 1974; Levin et al., 1978; Russo et al., 1984). Pharmacokinetic data have been published (Lee et al., 1985). It should be taken at least three hours after the last food intake.

Metabolism and excretion

CCNU rapidly disappears from plasma after oral or parenteral administration, and it has been assumed that its fate in vivo is similar to its decomposition in aqueous solution. Schemes for this decomposition, including suggested mechanisms for non-specific catalysis of decomposition by serum proteins have been published (Colvin et al., 1976) and these indicate the formation of chloroethyl carbonium ion as an alkylating agent, and cyclohexyl isocyanate as a carbamoylating agent. Excretion of radioactivity due to variously (ethylene, carbonyl, cyclohexyl) labeled CCNU is mainly in the urine. There is also some biliary excretion and reabsorption from the gastrointestinal tract in some species. Other urinary metabolites are cyclohexylamine and dicyclohexyl urea. In addition to these essentially hydrolytic products of CCNU metabolism, there has also been demonstrated in vitro monohydroxylation of the cyclohexyl ring by rat liver microsomes to yield cis- and trans- hydroxylated derivatives in position 2, 3, and 4 of the cyclohexyl ring (Hilton and Walker, 1975). The same hydroxylation has been found after parenteral administration of CCNU (reviewed by Kohlhepp et al., 1981); major urinary excretion products among these are the cis-4- and trans-4-hydroxylated products and these have also been demonstrated in plasma after ingestion of CCNU in man (Lee et al., 1985). The properties of some of these derivatives have been studied; they appear to be more toxic than CCNU but have better therapeutic indices. Their carbamoylating and alkylating properties differ from each other and from CCNU, depending on the position of the hydroxyl group (Johnston et al., 1975; Wheeler et al., 1977; Heal et al., 1978). Other urinary products of metabolism are thiol conjugates (thiodiacetic acid, S-carboxymethyl cysteine) derived from the alkylating species (Kohlhepp et al., 1981).

Side effects

Adverse events in man mainly affect the hematopoietic system with thrombocytopenia, leucocytopenia and anaemia. Myelosuppression occurs delayed, mainly after 4-6 weeks and can be cumulative. Further, medication with CCNU might lead to nausea and vomiting, more rarely to diarrhea. Occasionally, moderate hepatic dysfunction has been observed. In rare cases, pulmonary fibrosis, alopecia, stomatitis and minor neurological dysfunctions, e.g. apathia, ataxia and desorientation. In a few cases, irreversible damage of the optic nerve has been described in the combination with radiotherapy. CCNU can have carcinogenic, mutagenic and teratogenic effects.

2. OBJECTIVES

2.1 Primary Objective

This phase III trial determines whether combined CCNU/TMZ chemotherapy plus standard radiotherapy is superior to TMZ monochemotherapy plus standard radiotherapy alone in patients with newly diagnosed mMGMT GBM patients regarding overall survival.

2.2 Secondary Objectives

Secondary objectives are to determine whether combined CCNU/TMZ/RT therapy is superior to standard TMZ/RT therapy regarding progression-free survival and time to treatment failure as well as to determine acute and late toxicity of CCNU/TMZ therapy including its effects such as the delay of subsequent courses due to acute toxicity.

2.3 End-points

Primary end-point:

- Overall survival (OS) as measured from the day of randomization until death
-

Secondary endpoints:

- Progression-free survival (PFS) as measured from the day of randomization until diagnosis of progressive disease determined by MRI (modified RANO criteria)
- Best response rate determined by MRI (modified RANO criteria)
- Frequency of delay of the next CCNU/TMZ or TMZ course by more than 2 weeks
- Acute toxicity during radiotherapy and chemotherapy according to CTC AE V4.0
- Quality of life, determined by EORTC QLQ questionnaires
- Evaluation of late neurotoxicity by MMSE and NOA-07 test battery.
- Time to treatment failure

3. STUDY POPULATION

3.1 General Considerations

Newly-diagnosed patients with histologically proven glioblastoma or gliosarcoma and a methylated MGMT can be accrued for this trial. This accounts for 40-45% of the population of newly diagnosed GBM. Only patients without prior chemotherapy or radiotherapy may be included. Since the present trial compares experimental CCNU/TMZ with standard TMZ the inclusion/exclusion criteria are identical to the ones of the trial establishing TMZ as standard therapy (Stupp et al., 2005). This also implies that only adult patients up to an age of 70 years can be accrued.

3.2 Inclusion Criteria

Patients meeting **all** the following criteria may be enrolled

- Written informed consent
- Patients have to be in a cognitive state that allows them to understand the rationale and necessity of study therapy and procedures.
- Newly diagnosed histologically proven GBM or gliosarcoma WHO Grad IV, histology confirmed by reference neuropathology (Institute of Neuropathology, University of Bonn Medical Center, [name]. [name]). Histology obtained by complete resection, partial resection, open biopsy or stereotactic biopsy
- Methylated MGMT promoter in the tumor as determined by MDxHealth using methylation-specific PCR
- Males or females 18-70 years of age, estimated life expectancy of at least 12 weeks
- Karnofsky Performance Score (KPS) \geq 70%
- Patient compliance and geographic proximity that allow adequate follow up
- Male and female patients with reproductive potential must use an approved contraceptive method (intrauterine device, birth control pills, or barrier device) during and for 3 months after the trial (Pearl index $<$ 1%)
- Pre-menopausal female patients with childbearing potential: a negative serum pregnancy test must be obtained prior to treatment start

- Adequate organ function as described below:
 - Adequate bone marrow reserve:
 - white blood cell (WBC) count $\geq 3000/\mu\text{l}$,
 - granulocyte count $> 1500/\mu\text{l}$,
 - platelets $\geq 100000/\mu\text{l}$,
 - haemoglobin ≥ 10 g/dl
 - Adequate liver function
 - bilirubin < 1.5 times above upper limit of normal range (ULN),
 - alanine transaminase (ALT/SGPT) and aspartate transaminase (AST/SGOT) < 3 times ULN
 - Adequate renal function: creatinine < 1.5 times ULN
- Adequate blood clotting:
 - PT not below lower limits of normal range
 - PTT not exceeding the upper limit of normal range
- Negative HIV test

3.3 Exclusion Criteria

Patients meeting **one** of the following criteria **cannot** be enrolled:

- Prior malignancy (unless adequately treated carcinoma in situ of the cervix or nonmelanoma skin cancer), unless the prior malignancy was diagnosed and definitively treated at least 5 years previously with no subsequent evidence of recurrence
- Prior chemotherapy, systemic or local treatment with DNA-damaging agents, tyrosine kinase inhibitors or anti-angiogenic agents for any cancer
- Prior RT to the brain
- Concurrent administration of any other anti-tumor therapy not described in the protocol

- Allergy or intolerance of temozolomide, dacarbazine, CCNU or other nitrosourea derivatives
- Unable to undergo MRI
- Past medical history of diseases with poor prognosis, e.g. severe coronary heart disease, heart failure (NYHA III/IV), severe and poorly controlled diabetes, immune deficiency, residual deficits after stroke, severe mental retardation or other serious concomitant systemic disorders incompatible with the study (at the discretion of the investigator)
- Known HIV infection, active Hepatitis B or C infection
- Any active infection (at the discretion of the investigator)
- Female patients that are pregnant or breastfeeding
- Patients with reproductive potential who do not accept to use contraception during the trial and 3 months thereafter
- Treatment in another clinical trial with therapeutic intervention or use of any other investigational agent within the 30 days before enrolment
- Any psychological, cognitive, familial, sociological or geographical condition potentially hampering compliance with the study protocol and follow-up scheduled visits (at the discretion of investigator)

3.4 Distribution of gender

In the previous trial defining the standard for first-line treatment of glioblastoma (Stupp et al., 2005), 61% male and 39% female patients had been included. Since the present CeTeG trial uses the same inclusion criteria and thus addresses the same population, a similar distribution of gender can be expected. Gender is not a prognostically significant marker in glioblastoma so that there will be no stratification according to gender and no subgroup analyses according to gender. Population pharmacokinetic analysis indicates that women have an approximately 5% lower clearance adjusted for body surface area for temozolomide than men. Women have higher incidences of Grade 4 neutropenia and thrombocytopenia in the first cycle of therapy than men. Overall, the differences

between the two genders are so small that all patients receive TMZ doses irrespective of their gender.

3.5 Removal of subjects from study / Withdrawal of subjects

An individual patient will be discontinued from study therapy within the study but treated off-study and followed further under the following circumstances:

- There is MRI- defined progressive disease according to modified RANO criteria as determined by central reference neuroradiology
- The patient requests discontinuation.
- The drugs exhibit unacceptable toxicity defined as follows:
 - Delay of the next course for 6 weeks or more due to hematological toxicity
 - Any non-hematological CTCAE grade 3/4 toxicity attributable to CCNU or temozolomide. Those patients may receive temozolomide or CCNU monotherapy, respectively, if toxicity can be clearly attributed to one of the agents
- The patient becomes pregnant.
- Non-compliance

When a patient withdraws prior to completing the study, the reason for withdrawal is to be documented on the CRF and in the source document. Any clinically significant abnormalities persisting at withdrawal will be followed by the investigator until resolution or until reaching a clinically stable endpoint.

All patients who are discontinued from study therapy for any reason have to be followed according to the study protocol with clinical and MRI investigations (see chapter 6.1."Follow-up after completion of the study therapy or withdrawal (every 12 weeks)") until the end of the follow-up-time of the whole trial 3 years after the inclusion of the last patient.

If a patient requests discontinuation of the study therapy and withdraws his/her consent for the trial, the patient is asked to consent to the performance and documentation of the follow-up visits according to the study protocol.

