
Discontinuation rules
	
Discontinuation of the whole trial
 
 • The trial will be stopped in case of unacceptable toxicity. Unacceptable toxicity is found if more than 2 of the first 30 patients in one of the arms of the trial die from acute complications of therapy. • Additionally, the DMSB and/or the coordinating investigator as the designee of the sponsor can stop the trial transiently or permanently for any safety reason. • There is no interim analysis for efficacy. Thus there is no stopping rule based on efficacy parameters. 
Discontinuation rules for an individual patient. An individual patient will be discontinued from study therapy under the following circumstances:
 
 • There is MRI- defined progressive disease according to modified RANO criteria. • The patient requests discontinuation (as long as the patient consents explicitly for further follow-up): 
 ▪ Non-compliance of the patient • The drugs exhibit unacceptable toxicity: 
 Delay of the next course for 6 weeks or more due to hematological toxicity Any non-hematological CTCAE grade 3/4 toxicity attributable to CCNU or temozolomide. Those patients may receive temozolomide or CCNU monotherapy, respectively, if toxicity can be clearly attributed to one of the the agents • The patient becomes pregnant

Statistical analysis
	
Efficacy: Overall survival (OS) as primary efficacy parameter is measured from the day of randomization into one of the study arms until death. OS will be compared between the two treatment groups using a two-sided log-rank test at a level of 5% stratified for center and GBM recursive partitioning analysis (RPA) class.
 
Description of the primary efficacy analysis and population: The primary analysis will be performed according to the intention to treat (ITT) principle. The intent-to treat (ITT) analysis includes all 128 patients who have been randomized in the trial and have started with the first dose of CCNU (experimental arm) or TMZ

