Before start of chemotherapy (concomitant TMZ or first cycle CCNU/TMZ: blood analysis obtained in Baseline can be used if not longer than 5 days old)

 - Assessment of survival
 - vital signs,
 - physical and neurological examination,
 - concomitant medication,
 - Karnofsky PS,
 - complete blood count and CRP,
 - serum chemistry and urine analysis,
 - coagulation,
 - CTCAE evaluation

Throughout all treatment courses of TMZ and CCNU/TMZ starting with radiotherapy a differential blood count has to be determined weekly by the general practitioner of each patient. The results have to be faxed within 24 hours to the treating center for review. In case pathological laboratory values are regarded by the local investigator to have medical consequences (e.g. grade 4 neutropenia requiring prophylactic antibiotic treatment) the differential blood count has to be repeated at the study center.

- **MRI/ progression assessment visits every 12 weeks (+/- 5 days) after randomization during study treatment and follow up until end of study**
- (Follow-up of all patients ends 36 months after the inclusion of the last patient. All patients in the trial are followed until this time point.)
 - vital signs
 - physical and neurological examination

- concomitant medication (all medication during the treatment phase, during follow-up this includes only the tumor-related medication)
- further tumor-directed therapy (surgery, radiotherapy, chemotherapy): day of start of further therapy, day of progression for each therapy
- Karnofsky PS
- Mini-Mental-Status evaluation
- quality of life questionnaire
- contrast-enhanced MRI scan
- NOA-07 test battery (only every 24 weeks)
- complete blood count and CRP
- Blood sampling for translational studies
- serum chemistry and urine analysis
- coagulation
- CTCAE evaluation
- Assessment of progression/survival

Table 2: Schedule of Study procedures

	Screening visit Week 1-3	Baseline visit Week 3-5 ⁽²⁾	Treatment phase		After 6 courses of CCNU/TMZ or TMZ
			At the beginning of each course of CCNU/TMZ or TMZ	MRI/progression assessment visit every 12 weeks ⁽¹⁾	MRI/progression assessment visit every 12 weeks ⁽¹⁾
Clinical examination					
Informed consent for MGMT and reference neuropathology ⁽³⁾⁽³⁾	x				
Informed Consent for trial participation		x			
Results of MGMT testing and ref. neuropathology		x			
I / E criteria, demographics and medical history		x			
Evaluation of preexisting conditions in analogy to CTCAE		x			

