The assumptions for the initial planning of the trial match to event (death) rates of 0.356 and 0.176 events per patient year and result in an expected number of 68 events after two years of recruitment and two years of follow-up. . A blinded analysis of the overall survival time 14 months after last-patient-in (36 months after first-patient-in) showed that there is an overall mean risk for the event “death” of 0.1994/patient year due to an unexpected low number of events at this time and indicating a low number of events at the end of the intended follow-up-time which might result in a power lower as expected. With the observed actual event rate and an assumed OR of 2 as planned, the 68 events required for an analysis with a sufficient power of 80% can be reached by a prolongation of the follow-up time to April 2017, i.e. 36 months after last-patient-in. The sample size calculation was performed using the “PS” power and sample size program (Dupont and Plummer, 1997) and additional simulation analysis. Assuming that 6% of patients may not be analyzable for the primary endpoint OS due to non-compliance or loss to follow-up before the start of chemotherapy, additional 8 patients adding up to a total of 136 MGMT-methylated patients have to be randomized for the trial. Dropout patients and patients lost for follow-up after the start of chemotherapy will be evaluated as observations censored at the time of dropout. The figure of approx. 6% patients who may be non-compliant and/or lost for follow-up for the ITT evaluation of the primary endpoint may be overestimated. In the previous bicentric phase II trial with CCNU/TMZ ([name] et al., 2006; Glas et al., 2009), none of the 31 patients included was lost for follow-up or non-compliant. This corresponds to experiences of most centers with other trials for untreated GBM such as the so far not published phase II cilengitide trial. In experienced neurooncological centers as the ones taking part in the CeTeG trial, the lost-to-follow-up rate is very low. The long-term analysis of the EORTC/NCIC trial

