Written informed consent in the CeTeG trial is obtained in two steps. First, at the screening visit, patients are asked to consent to reference neuropathology and MGMT testing. In the second step after obtaining the results of reference neuropathology and MGMT promotor methylation analysis, patients are asked to consent to participation in the trial.

In case the patient wants to withdraw from study treatment he will be asked to consent to continuation of monitoring of disease progression every 12 weeks as planned in this study and as standard in routine patient care.

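### A patient who withdraws and declines the 12-weekly follow-up is offered no survival-status-only step, so the protocol gives no route to the date of death for the primary endpoint

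*Protocol*

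**What the plan says.** **Stopping therapy.** Protocol section 3.5 requires everyone taken off study therapy, for whatever reason, to be followed clinically and by MRI until the whole trial's follow-up ends, 3 years after the last inclusion.

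**Withdrawing consent.** The next paragraph of 3.5 covers a patient who asks to stop and also withdraws consent: "the patient is asked to consent to the performance and documentation of the follow-up visits according to the study protocol". Section 11.5, worded for a patient who wants to withdraw from study treatment, says "he will be asked to consent to continuation of monitoring of disease progression every 12 weeks as planned in this study" and adds that such monitoring is routine care. The synopsis attaches a condition to discontinuation at the patient's request: "as long as the patient consents explicitly for further follow-up".

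**What follow-up consists of.** Section 6.1 schedules "MRI/ progression assessment visits every 12 weeks (+/- 5 days) after randomization". Each visit includes physical and neurological examination, Karnofsky score, MMSE, quality of life, contrast MRI and blood tests, with the NOA-07 battery every 24 weeks. Once treatment courses have ended, vital status is collected as one item of this visit: "Assessment of progression/survival".

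**Endpoint and censoring.** Section 6.2.2 defines OS as time from randomization to death from any cause. The synopsis and sections 9.1 and 9.3 censor dropouts at the time of dropout. Section 9.1 moved the cut-off to 36 months after last-patient-in to reach "the 68 events required for an analysis with a sufficient power of 80" percent.

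**The concern.** The primary endpoint needs very little from a patient: whether and when death occurred, or the last date known alive. The withdrawal sections ask only for something heavier. A patient who would accept a telephone call but not 12-weekly visits is never asked about the call, and under the dropout rule that patient's OS ends at withdrawal.

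Two things are at stake. Some deaths are lost from a design whose cut-off was set to reach the required number. More importantly, withdrawal may be related to prognosis or to arm. The trial is open-label, and section 11 expects more myelotoxicity with CCNU/TMZ. If patients who are doing badly leave one arm more often, censoring them at withdrawal biases the comparison. A statistical analysis plan cannot recover dates that were never collected, so the remedy belongs in the protocol and the consent process.

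**Working it through.** **1. The plan's own figure (section 9.1).** Inputs: 2-year survival 48.9% and 70%, 64 patients per arm, 2 years of accrual, two-sided 5% level.

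- Rates: −ln(0.489)/2 = 0.358 and −ln(0.70)/2 = 0.178 per year (stated 0.356 and 0.176); hazard ratio (HR) 0.499.
- Expected deaths per arm with accrual R and further follow-up F: n·[1 − (e^(−λF) − e^(−λ(F+R)))/(λR)].
- With R = 2 and F = 2: 41.6 + 26.3 = 68.0 deaths (stated 68).
- Power by Schoenfeld's formula, Φ(|ln HR|·√d/2 − 1.96), at d = 68: 81.9% (stated 80%). The plan's figure is reproduced.

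**2. The current cut-off.** Inputs: observed pooled rate 0.1994 per year and ratio 2 (9.1). Splitting the rate evenly gives 2 × 0.1994/3 = 0.1329 and twice that, 0.2659. With R = 2 and F = 3, expected deaths are 41.6 + 26.3 = 67.9 and power is 81.5%. On the plan's 2-year accrual there is no surplus over 68. The count depends on accrual: 22 months (36 − 14, from the timing of the blinded look in 9.1) gives 67.1 deaths, and 35 months (one of the synopsis figures) gives 72.3.

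**3. Deaths and power lost.** Suppose a share s of patients has all deaths lost, at average prognosis. This is close to an upper bound, because deaths before withdrawal would still be counted.

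| s | Deaths left | Power (HR 0.50) |
|---|---|---|
| 0 | 68 | 81.5% |
| 1.6% (9/573, cited in 9.1) | 68 × 0.984 = 66.9 | 80.9% |
| 5% | 68 × 0.95 = 64.6 | 79.5% |
| 6% | 68 × 0.94 = 63.9 | 79.1% |

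The 6% row is for scale only. In 9.1 that figure is the allowance for loss before chemotherapy, and those patients are already outside the 128.

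**4. Bias, by simulation.** Assumptions: the rates in step 2, 136 patients, withdrawal at a uniform time within 0.7 years, withdrawers at twice their arm's hazard. None of the withdrawal inputs comes from the protocol except the 1.6%.

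| Who withdraws | HR, deaths known | HR, deaths lost |
|---|---|---|
| 6% of each arm | about 0.50 | about 0.50 |
| 1.6% overall, all in the experimental arm | 0.51 | 0.50 |
| 12% of the experimental arm, none in the other | 0.55 | 0.51 |

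The even split moves the estimate only in the third decimal. The last row is about 8 of 68 patients and favours CCNU/TMZ.

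**The case against.** The strongest objection is that the sections are silent on partial consent rather than hostile to it. A reader might infer an all-or-nothing rule in which refusing MRI or neuropsychological testing itself ends OS follow-up. The documents do not support that. Section 3.5 says what the patient is asked, not that partial consent is turned down, and nothing forbids obtaining a death date elsewhere. The consent pages were not available for this review, so a vital-status consent may exist there. Section 11.5 also asks for less than the full visit set and calls the monitoring routine care, and section 11.7 lists 12-weekly contrast MRI among standard procedures paid by health insurers. The extra burden of staying in is therefore smaller than the visit list suggests. All of this stands and narrows the point. It does not supply a survival-only step: progression monitoring is MRI-based, and the protocol sets out no other route to vital status.

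The patient register in 11.5 is said to serve long-term follow-up if needed. That shows tracing was foreseen, but no vital-status procedure or use after withdrawal is attached to it.

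The expected numbers are small. Section 9.1 cites 9 of 573 patients refusing further involvement in the EORTC/NCIC trial, and none of 31 lost or non-compliant in the phase II trial. This limits the power argument almost entirely. It limits the bias argument less, because bias depends on who withdraws and from which arm.

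Finally, part of the harm comes from the rule of censoring at dropout. The two are linked, but changing that rule alone would not help where the death date was never collected.

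**Conclusion.** The point holds in a limited form. For a patient who withdraws and also declines the visits or monitoring, the protocol provides no survival-status-only step, and its dropout rule then ends that patient's OS follow-up. Patients who only stop therapy are outside the point, because section 3.5 requires their follow-up to continue.

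At the cited 1.6% refusal rate the cost is about 1 death in 68 and at most about 1 point of power. That rests on exponential survival, the pooled rate of 0.1994 with ratio 2, 2 years of accrual and an unstratified test. Power is not the main reason to act.

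The main reason is possible prognosis-related censoring in an open-label trial, and its size cannot be derived from the documents. A reader might take the shift in HR from 0.55 to 0.51 as the expected bias. It is not: it needs 12% withdrawal in one arm, none in the other and a doubled hazard, and the protocol supports none of these. With balanced withdrawals the effect is negligible. This is a worthwhile, inexpensive protection of the primary endpoint, not a defect that invalidates the analysis.

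**What to change.** In sections 3.5 and 11.5, and in the consent form if it lacks this, add:

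- A patient who declines the visits or the progression monitoring is asked for consent to survival status only. It is obtained by telephone from the patient, family or general practitioner at set intervals, for example every 12 weeks, and once at the 36-month cut-off.
- Declining visits or MRI does not end OS follow-up. Only refusal of survival contact does.

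**Cost.** An amendment with ethics approval (section 13.1), consent from the patients concerned, including for contact with family or general practitioner, and a few calls for each such patient. No visits, procedures or patients are added. The gain is limited at this stage: section 9.1 shows that recruitment was complete and a blinded look had been taken 14 months after last-patient-in, so some withdrawals will already have occurred, and those patients would have to be approached again.
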